- 5. Associated syndrome, including Marfan Disease or Neurofibromatosis
- 6. Sanders bone age greater than 4
- 7. Thoracic curve less than 35 degrees
- 8. Lumbar curve greater than or equal to 35 degrees
- 9. Unable or unwilling to firmly commit to returning for required follow-up visits
- 10. Investigator judgement that the subject/family may not be a candidate for the intervention

Number Of Subjects

Study Duration

Study Phases:

Screening

Study Treatment

Post-op Follow-Up

The study will be conducted at The Nemours – Alfred I duPont hospital for Children, Division of Orthopedics. Subject inclusion will be based on interest of patients that satisfy the inclusion/exclusion criteria that present to the Orthopedic Clinic. The total study enrollment will be 30 subjects. In the retrospective arm we will aim to enroll all patients who had the tether surgery in the past. The study ends when all patients reach skeletal maturity. Each subject's active participation will last about 5 years after surgery. The entire study is expected to last at least 8 years.

- 1. Screening phase: Subjects will be screened by study staff during a clinical visit in the Orthopedics department. Eligible subjects will be approached and if interested, enrolled during a routine clinical exam.
- 2. Study Treatment: The subject will undergo surgical intervention using accepted standard-of-care anterior approach using the Globus Medical Inc. CreoTM Stabilization System. Vertebral body tethering using screws and Polyethylene Terepthalate cord (Globus Medical, Inc. Reflect/TransitionTM Stabilization System) is investigational.
- 3. Post-operative Follow-up: Subjects will be followed at regular time points at 45 and 90 days post-op during the post-operative phase. Patients will also be seen at visits 180, 365, 730, 1095, 1460, 1825 days post-op during the extended follow-up phase.

Efficacy Evaluations

The primary efficacy evaluation measurement is thoracic Cobb angle (to nearest degree) at the pre-operative visit to Cobb angle during follow-up, especially at two years post-op (POD 730).

Safety Evaluations

We will use phase-specific endpoints to measure safety: 1) Study treatment phase: Any individual-level intraoperative events including neuromonitoring events (loss or change in neurological signaling or function), unanticipated events during surgery, and SAEs.

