- 2) Post-operative active phase: Incidence of infection (within 90 days post-op), pneumothorax, bronpulmonary plug, or any reportable SAE.
- 3) Extended follow-up phase: Incidence of over-correction, implant failure (measured on serial x-ray), incidence of curve progression to >50 degrees at 5 year follow-up, or incidence of secondary surgery or re-operation to correct further spine deformity (not related to trauma or other issues not related to the initial surgery / disease).

Statistical And Analytic Plan

Cobb angle is a continuous variable. T-test or repeated measures Anova will be used to detect any change in Cobb angle post-operatively. Linear regression will be utilized to assess which variables are associated with change in post-operative Cobb angle.

DATA AND SAFETY MONITORING PLAN

The PI and Data Safety group will meet regularly to discuss any safety events. Group's reports will be forwarded to the IRB during continuing review per ORC monitoring guidance. Safety reporting will be according to IRB SOP 408 and governing FDA guidelines. The PI and study team will also comply with all ORC monitoring standards. The PI will meet with the study team regularly to discuss study progress and ensure data fidelity. The first meeting will take place before initiation of the study to discuss the protocol and establish guidelines to monitor the study. The Sponsor-PI will work in conjunction with the DSMB members to prepare an agenda to address the review of the initiation of the trial, reporting of adverse events, stopping rules, etc.

Meetings will be held before enrolling the 1st, 5th, 9th and so forth patient. If a Serious Adverse Event (SAE) occurs, a separate meeting will be held.

The meetings will be held at the Nemours AIDHC Department of Orthopedics using WebEx connectivity for attendees who are not in the office.

Meeting minutes will be recorded by the study coordinator and will become part of the study binder.

DSMB group includes the following members who do not have a financial or other types of conflict of interest related to this study:

- 1. [name] [name]
- 2. [name]
- 3. [name], [name]

[name] will not lead the DSMB meetings, but help to prepare reports/events for the DSMB. [name] will be present as a participant in the meetings to answer questions by the DSMB personnel, but will not be present for a closed portion of the meeting.

Members of the DSMB are:

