3.3.2 Total Number of Study Sites/Total Number of Subjects Projected

The study will be conducted at Nemours – Alfred I duPont Hospital for Children. As this is a registry of an approved device being used in an off-label method, we do not have a maximum number of patients or target enrollment. Based on a broad review of patient visits over the past year, we may expect to enroll up to 15 patients per year. These patients will be followed up clinically until skeletal maturity. The total number of enrolled subjects in both retrospective and prospective arms will be 30.

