6.6.2 Stopping rules for SAEs that are device-related
Definition of Terms:
□ Screw failure – screw and/or centering staple have loosened from the vertebra AND require re- operation
☐ Tether failure – the tether has broken or lost tension. Diagnosed at any time point after 3 months by increased angulation at a disc space on standing PA or increase in disc wedging on side bending x-ray to the side away from the implant. Also, it is only an SAE if noted before maturity AND overall Cobb worsens compared to the first erect measurement
☐ Implant re-operation - any problem with the implant that requires re-operation including re-operation for overcorrection with any of the following: a removal of all or part of the implant, loosening of the tension on the implant, or spinal fusion.

Stopping Points
☐ Screw failure stopping point: 3 of first 5 cases, 5 of first 10, or 25% of patients beyond 20
cases
☐ Tether failure stopping point: 3 of first 5 cases, 5 of first 10, or 25% of patients beyond 20
cases
☐ Implant failure re-operation stopping point: occurs in 4 of first 5 cases or greater than 50% of
cases beyond 10 cases

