8.4 Recording plan for AE / SAEs

Surgery and Post-operative Phase (Day 0 – POD 90):

For these phases, all AEs (including SAEs) will be noted in the study records and reported per IRB and FDA requirements outlined below. The subjects will be encouraged to contact the office with any concerns, and the medical record will be monitored by study staff for indications of AEs.

Extended Follow-up Phase (POD 91-POD 1825):

For this phase, all SAEs will be recorded (regardless of cause). Only AEs which are deemed "device related" will be recorded on study documents and reported per IRB and FDA requirements outlined below. The subjects will still be encouraged to contact the office with any concerns, and the medical record will be monitored by study staff for indications of SAEs or device-related AEs.

Only the AE/SAEs indicated above will be recorded in a patient-specific study binder, kept in the secure Orthopedics research office. The binder will contain a full description of the event, including the nature, date and time of onset, determination of non-serious versus serious, intensity (mild, moderate, severe), duration, causality, and outcome of the event. Hard copies of the primary documents (medical record notes) describing the event and any associated treatment will be printed and kept in the patient-specific study binder. A redundant copy of adverse events will be kept in the study REDCap database and will be maintained by the study team separately from the patient-specific study binder. The study binder will serve as the official record of all Events.

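### The implant re-operation stopping limit has no follow-up condition, so late re-operations are diluted by recently operated children and the limit reacts later than it reads

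*Combined protocol and SAP*

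**What the plan says.** Section 6.6.2 defines implant re-operation as "any problem with the implant that requires re-operation including re-operation for overcorrection with any of the following": removal of all or part of the implant, loosening of its tension, or spinal fusion. Over-correction is therefore covered. The limit reads "Implant failure re-operation stopping point: occurs in 4 of first 5 cases or greater than 50% of" cases beyond 10 cases.

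No limit in 6.6.1 or 6.6.2 states a follow-up time that a child must reach before entering the denominator. The nearest provision concerns when a tether failure may be called: "Diagnosed at any time point after 3 months by increased angulation at a disc space on standing PA". That times a diagnosis and does not say who is counted.

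The synopsis lists these outcomes under late follow-up: "Extended follow-up phase: Incidence of over-correction, implant failure (measured on serial x-ray"), together with re-operation for further deformity. Section 8.4 (recording plan) dates that phase: "Extended Follow-up Phase (POD 91-POD 1825").

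On accrual, section 3.3.2 says "we may expect to enroll up to 15 patients per year" and "The total number of enrolled subjects in both retrospective and prospective arms will be 30". The synopsis says "The entire study is expected to last at least 8 years", with about 5 years of participation per child after surgery. Section 6.5 gives the rules one consequence, a halt to enrolment. No wait between cases is stated.

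**The concern.** A limit expressed as a share of cases works as read only if each case has had time to have the event. Over-correction and the re-operations that follow are looked for after day 90, and the animal work in section 1.3.2 reports induced deformity rising with the time the tether is in place. While enrolment is open, many operated children cannot yet have had the event, yet all of them count in the denominator.

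An illustration, at 15 a year and a 12-month lag: case 26 is due, 25 children are operated, and 11 have 12 months of follow-up. Six of the first 10 have been re-operated, three of them among the first 5. That is 6/11 = 55% of those followed, but the over-50% part sees 6/25 = 24%, and neither 4 of first 5 nor 7 of first 10 is met. Since the only action is to stop enrolling, a trigger met late spares few children. Safety is the trial's primary objective, and this use of the implant is investigational.

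**Working it through.** Section 6.4 gives no power analysis, and no performance figure is stated for the stopping rules, so there is none to reproduce.

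**Inputs**
- From the documents: 15 a year (3.3.2, an upper expectation), 30 cases (3.3.2), and the limits in 6.6.1 and 6.6.2.
- Slower alternative: 8 years less 5 years of follow-up leaves 3 years, and 30/3 = 10 a year.
- Assumed: evenly spaced cases, all 30 prospective, a lag from surgery to re-operation of 0 to 24 months, and the over-50% part read as cumulative.

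**Count at 15 a year**
- Spacing is 12/15 = 0.8 months.
- When case n is due, n − 1 children are operated. Child i is 12 months out if (n − i) × 0.8 ≥ 12, so n − 15 children are.
- The over-50% part needs floor((n − 1)/2) + 1 events.
- n = 20: 10 events among 5 children, impossible. n = 25: 13 among 10, impossible. n = 29: 14/28 = 50.0%, not above the limit. n = 30: 15/29 = 51.7%, which needs 15 of 15.
- 4 of first 5 needs n − 15 ≥ 4, so n = 19. 7 of first 10 needs n − 15 ≥ 7, so n = 22.

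Events that the over-50% part needs among children operated long enough ago:

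| Accrual, lag | Case 20 due | Case 30 due |
|---|---|---|
| 15 a year, 3 months | 10 of 16 (63%) | 15 of 26 (58%) |
| 15 a year, 6 months | 10 of 12 (83%) | 15 of 22 (68%) |
| 15 a year, 12 months | impossible | 15 of 15 |
| 15 a year, 24 months | impossible | impossible |
| 10 a year, 12 months | 10 of 10 | 15 of 20 (75%) |

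**Chance of a halt before the last case**

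Simulation: 100,000 runs, independent cases, rules checked when each next case is due. Each re-operation also counts as an SAE under 6.6.1. There are no other SAEs and no screw or tether failures. True re-operation rate 60%, 15 a year. The last column adds the check given under the fix, without any hold.

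| Lag | Printed rules | With added check |
|---|---|---|
| Known at once | 94% | 94% |
| 6 months | 54% | 84% |
| 12 months | 47% | 85% |
| 13 months | 47% | about two-thirds |
| 15 months | 47% | 47% |
| Spread evenly over 3–24 months | 26% | 40% |
| 24 months | 0% | 0% |

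- At 12 months almost all of the 47% comes from 4 of first 5 and 7 of first 10. The over-50% part needs all 15, with chance 0.6^15 = 0.0005.
- At 10 a year and 12 months: 48% printed, 89% with the check.
- With other SAEs in an assumed 10% or 20% of children, the printed 47% becomes 55% or 67%.

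**When the added check starts**

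It needs 11 children at POD 365. At 15 a year, n − 15 = 11 gives case 26. At 10 a year (spacing 1.2 months, n − 10 children at 12 months) it gives case 21.

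**The case against.** Several objections have force.

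- **The other part of the limit.** A reader might infer that the re-operation limit as a whole is inert until case 30. It is not. The same line also stops at 4 of first 5, which in the 12-month scenario can act from case 19, with 12 children still to be operated.
- **The inputs.** Fifteen a year is an upper expectation. At 10 a year the over-50% part can be met from case 20. The 12-month lag is assumed: the documents give no over-correction rate or timing, and the animal data do not date re-operation in children. Section 3.3.2 also disclaims a target enrolment before stating 30.
- **Retrospective children.** The 30 includes them, and their events may already be known. If they count as cases, the dilution is smaller.
- **The illustration.** It sits one event short of both 4 of first 5 and 7 of first 10. One procedure-related SAE in any of the other four of the first 10 children would meet 6.6.1.
- **The DSMB.** It meets before the 1st, 5th, 9th patient and so on. Re-operation under general anaesthesia is Clavien-Dindo grade IIIb, hence an SAE, and each SAE brings a separate meeting. Six re-operations would mean six such meetings.

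These points limit the size of the problem and rule out a claim that children are unprotected. They do not remove it. The over-50% part is the only part of the re-operation limit that looks beyond the first 5 cases. Even at a 6-month lag it asks for 83% of the children operated long enough ago when case 20 is due. Discretionary review does not make up for a written trigger that reads as not met.

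**Conclusion.** The point holds as a weakness in how the limit is counted. The level of tolerance (4 of 5, more than 50%) is the sponsor's clinical choice and is not disputed. At a true rate of 60%, above the printed limit, the chance of a halt at 15 a year falls from about 94% with immediate events to 54%, 47% and 26% for lags of 6 months, 12 months and 3 to 24 months.

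These figures rest on the assumed lag, even spacing and 30 prospective cases. With 25 or 20 prospective cases the over-50% part cannot be met at 12 months, and the halt probability is 47% or 34%. If the over-50% part covers only cases after the 10th, it would be weaker still: (N − 25)/(N − 10) > 0.5 needs N > 40. The documents do not support a reading that over-correction is outside the rules, that a 60% rate is expected, or that nothing could stop enrolment before case 30.

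**What to change.** Keep the printed limits. Add to 6.6.2: *The >50% re-operation limit is also checked among children who have reached POD 365, once more than 10 have done so.* State there whether retrospective children count as cases.

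This costs one sentence and one clarification, with no new data and no pause in accrual. The price is a somewhat higher chance of a pause at lower true rates. At a 12-month lag and 15 a year it is about 1.4% instead of 0.6% at a 19% rate, and 11% instead of 3.6% at 30%. With events known at once the printed rules give 1.5% and 12%, so the tolerance is restored rather than tightened.

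The limits of the fix should be stated. At 15 a year the check first applies when case 26 is due, so it can spare at most the last five children, and it adds nothing with 25 or fewer prospective cases. It gives almost no gain for lags of 15 months or more at that pace. POD 365 visits have a 90-day grace period, so some detections will fall in that range.

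An optional extra, for the sponsor to weigh, is to hold case 21 until 11 children have reached POD 365. At 15 a year child 11 is operated at 10 × 0.8 = 8.0 months and reaches 12 months at 20.0. Case 21 is due at 20 × 0.8 = 16.0 months, so the hold is 4.0 months; at 10 a year there is none. With it the halt probability is 89% at 12 months, about 75% at 13 and 55% at 15. At 12 months the mean number operated before a halt falls from 25.3 under the printed rules to 21.2. For re-operations at 24 months even the hold gives almost no protection at 15 a year; only slower enrolment would.

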7 STUDY DEVICE

7.1 Description

The device is the use of Polyethylene Terephthalate (PET) cord with pedicle screws and staples for vertebral body tethering. The PET cord is part of a 510k-cleared implant system distributed by Globus Medical, Inc. called the Reflect/TransitionTM Stabilization System. The pedicle screws and staples are part of a 510k-cleared implant system distributed by Globus Medical, Inc. called the CREOTM Stabilization System. Both systems are classified as Class II under 21 CFR 888.3070, and are manufactured and distributed according to manufacturer guidelines and in compliance with 21 CRF 820. The combined use of screws, staples, and Polyethylene Terephthalate cord for vertebral body tethering is investigational.

The entire system is supplied at Nemours as part of routine surgical treatment. The system supplied also includes hydroxyapatite-coated titanium alloy Ti6Al4V (ASTM F136) or alloy Ti6Al4Nb (ASTM F1295) pedicle screws, polycarbonate urethane spacers and bumpers, titanium alloy spools, end spools, and set screw ends. The only article being used from this system is the PET cord. The rest of the system will be discarded according to the appropriate NEMOURS Operation Room policies and procedures.

7.2 Packaging

The device is part of a commercially marketed system from Globus Medical, Inc. As such, the device is packaged according to manufacturer guidelines and in compliance with 21 CFR 820.130.

7.3 Labeling

The device is part of a commercially marketed system from Globus Medical, Inc. As such the device will be labeled according to manufacturer guidelines and in compliance with 21 CFR 801. Specific device label parameters will be tracked by the study team to comply with FDA standards for investigational device tracking. Those parameters include:

- o Manufacturer of device
- o Model name of device
- o Device Part Number
- o Device Lot Number
- o Unique Device Identification (UDI)
- o Length of PET cord used

All parts of the tethering system (vertebral screws, set screws, staples and PET cord) will be labeled and tracked in the same manner.

8 SAFETY MANAGEMENT

8.1 Clinical Adverse Events

Clinical adverse events (AEs) will be monitored throughout the study.

8.2 Adverse Event Reporting

Unanticipated problems related to the research involving risks to subjects or others that occur during the course of this study (including SAEs) will be reported to the IRB in accordance with Nemours IRB SOP 408: Unanticipated Problems Involving Risks to Subjects. AEs that are not serious but that are notable and could involve risks to subjects will be summarized in narrative or other format and submitted to the IRB at the time of continuing review.

8.3 Definition of an Adverse Event

An adverse event is any untoward medical occurrence in a subject who has received an intervention (drug, biologic, or other intervention). The occurrence does not necessarily have to have a causal relationship with the treatment. An AE can therefore be any unfavorable or unintended sign (including an abnormal laboratory finding, for example), symptom, or disease temporally associated with the use of a medicinal product, whether or not considered related to the medicinal product.

We will use the Clavien-Dindo Classification system [47], as well as the Comprehensive Complication Index (based off of the Clavien-Dindo system) [48] to classify and analyze patient adverse events. **Grade I and Grade II events will be considered AEs.** (See Appendix 1 for classification table)

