8.4 Definition of a Serious Adverse Event (SAE)

An SAE is any adverse event that results in any of the following outcomes: □ death,
$\ \square$ a life-threatening event (at risk of death at the time of the event),
$\hfill \Box$ requires in patient hospitalization or prolongation of existing hospitalization,
$\hfill\Box$ a persistent or significant disability/incapacity, or
$\hfill \square$ a congenital anomaly/birth defect in the offspring of a subject.
Important medical events that may not result in death, be life-threatening, or require hospitalization may be considered a serious adverse event when, based upon appropriate medical judgment, they may jeopardize the subject and may require medical or surgical intervention to prevent one of the outcomes listed in this definition.

A distinction should be drawn between serious and severe AEs. A severe AE is a major event of its type. A severe AE does not necessarily need to be considered serious. For example, nausea which persists for several hours may be considered severe nausea, but

would not be considered serious. On the other hand, a stroke that results in only a limited degree of disability may be considered a mild stroke, but would be considered serious. We will use the Clavien-Dindo Classification system [47], as well as the Comprehensive Complication Index (based off of the Clavien-Dindo system) [48] to classify and analyze patient adverse events. Grade III (a/b), Grade IV (a/b), and Grade V events will be considered SAEs. (See Appendix 1 for classification table)

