To monitor for surgery risks related to neurology there will an Intra-operative Neuromonitoring in the Operating room. After surgery, the patient will be monitored for pneumothorax by inpatient hospital staff. If a pneumothorax is found, it may cause elongation of the patient's hospital stay, or require medical / surgical intervention. After surgery, the patient will be monitored for presence of a bronchopulmonary plug by inpatient hospital staff. If a bronchopulmonary plug is found, it may cause elongation of the patient's hospital stay, or require a medical / surgical intervention. Nemours uses low dose x-ray machine for all spinal x-rays to reduce the amount of radiation patient receives. The widely-accepted ALARA (as low as reasonably acceptable) principle will be used to ensure surgeons are imparting the lowest radiographic dose possible onto the patient during fluoroscopy.

4. Spine surgery risks

Your Nemours surgeon- [name]- is a pediatric spine surgeon who performs an average of 50 spine surgeries per year. His assistants are clinical fellows who are board certified orthopedic surgeons. They will use their knowledge and skills to eliminate or minimize any of the surgery related risks.

5. Other Potential Risks 9.3.2.2 (No greater than minimal risk study procedures)

- Nemours make all efforts to protect patient's privacy. Study data are stored in locked cabinets and password protected computers.
- Subjects will be allowed to skip questions which they are not comfortable answering without compromising their participation in the study.

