12 APPENDIX

12.1 Appendix 1: Clavien-Dindo complications classification system (from Dindo, et al.)

Grade	Definition		
Grade I	Any deviation from the normal postoperative course without the need for pharmacological treatment or surgical, endoscopic, and radiological interventions		
	Allowed therapeutic regimens are: drugs as antiemetics, antipyretics, analgetics, diuretics, electrolytes, and physiotherapy. This grade also includes wound infections opened at the bedside		
Grade II	Requiring pharmacological treatment with drugs other than such allowed for grade I complications		
	Blood transfusions and total parenteral nutrition are also included		
Grade III	Requiring surgical, endoscopic or radiological intervention		
Grade IIIa	Intervention not under general anesthesia		
Grade IIIb	Intervention under general anesthesia		
Grade IV	Life-threatening complication (including CNS complications)* requiring IC/ICU management		
Grade IVa	Single organ dysfunction (including dialysis)		
Grade IVb	Multiorgan dysfunction		
Grade V	Death of a patient		
Suffix "d"	If the patient suffers from a complication at the time of discharge (see examples in Table 2), the suffix "d (for "disability") is added to the respective grade of complication. This label indicates the need for a follow-up to fully evaluate the complication.		

^{*}Brain hemorrhage, ischemic stroke, subarrachnoidal bleeding, but excluding transient ischemic attacks. CNS, central nervous system; IC, intermediate care; ICU, intensive care unit.

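### Do the Clavien-Dindo labels in 8.3 and 8.4 leave it open whether a low-grade event that prolongs hospitalization is an SAE?

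*Combined protocol and SAP*

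**What the plan says.** Section 8.4 of the protocol opens with an outcome test: "An SAE is any adverse event that results in any of the following outcomes". One listed outcome is that the event "requires in patient hospitalization or prolongation of existing hospitalization". Later in the same section comes a grade test: "Grade III (a/b), Grade IV (a/b), and Grade V events will be considered SAEs". Section 8.3 supplies the other half of the grading: "Grade I and Grade II events will be considered AEs".

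Appendix 1 defines the grades by what was done for the patient. Grade I is "Any deviation from the normal postoperative course without the need for pharmacological treatment or surgical, endoscopic, and radiological interventions"; Grade II is "Requiring pharmacological treatment with drugs other than such allowed for grade I complications". Length of stay and readmission are not grading criteria.

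SAE status is used in three places:
- Section 6.6.1 counts procedure-related SAEs towards halting enrollment.
- The data and safety monitoring plan in the synopsis calls a separate DSMB meeting when an SAE occurs.
- The recording plan (also numbered 8.4) keeps all AEs through POD 90. After that it keeps only SAEs and device-related AEs.

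**The concern.** Take a complication that is only observed or treated with drugs but lengthens the stay or causes a readmission. By the outcome list it is an SAE. By the paired grade labels it looks like a plain AE. The protocol foresees such a case: of pneumothorax, section 9.3.2 says "If a pneumothorax is found, it may cause elongation of the patient's hospital stay", and it names medical or surgical intervention as the alternative.

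Nothing says in so many words which test prevails. The recording plan asks for a serious or non-serious entry for each event, and the case-by-case determination in 8.4.1 covers relatedness, not seriousness. If two coders classified such an event differently, three things could change: the 6.6.1 count, the calling of a separate DSMB meeting, and, after POD 90, whether a hospitalization unrelated to the device enters the adverse event record at all. The last is the most serious, because an event left out cannot be recovered from that record at analysis.

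**Working it through.** **Reading the passages together**

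1. The outcome test in 8.4 applies to any adverse event and carves out no grade. On its own it makes a Grade I or II event that prolongs hospitalization an SAE.
2. The sentence in 8.3 calls Grade I and II events AEs. It does not call them non-serious, or AEs only. Elsewhere the protocol uses AE as the umbrella term: the recording plan treats SAEs as included among AEs. When section 8.2 means the subset, it says so: "AEs that are not serious but that are notable and could involve risks to subjects".
3. Just before the grade sentence, 8.4 separates severity from seriousness. Its example is a stroke that may be called mild and is still serious. A low grade therefore does not cancel a listed outcome.
4. Grades III to V then act as a second route to SAE status.

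On this reading all three sentences hold at once, and the event is counted, recorded after POD 90 and sent to the DSMB.

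**What a misreading would do to the stopping rule**

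The documents give no SAE rate, so every rate here is assumed. The useful quantity is the difference between the two readings: the chance of a halt with and without the hospitalization-only events. The total of 30 in section 3.3.2 covers the retrospective and prospective arms together, so 30 is the upper limit for the number counted; 15 is shown as a smaller case.

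Let *p* be the per-patient probability of a procedure-related SAE, with patients independent, and let *P*ₙ(*k*) be the probability of *k* such patients among *n* without a halt so far:

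*P*ₙ(*k*) = *P*ₙ₋₁(*k*)(1 − *p*) + *P*ₙ₋₁(*k* − 1)*p*

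A halt occurs at *n* = 5 if *k* = 5, at *n* = 10 if *k* ≥ 7, and at any *n* ≥ 20 if *k* > *n*/2.

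Hand check at *p* = 0.20 with 15 patients, where only the first two rules can act: 0.2⁵ = 0.0003, and the probability of 7 or more in 10 is 0.0009. Their union, allowing for a small overlap, is 0.0011, as the recursion gives.

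Now add 2, 5 or 10 percentage points to *p* for patients whose only SAE would be a hospitalization-only event:

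| Base SAE rate | Patients | P(halt) at base | +2 points | +5 points | +10 points |
|---|---|---|---|---|---|
| 10% | 30 | 0.00% | 0.01% | 0.03% | 0.21% |
| 20% | 30 | 0.21% | 0.43% | 1.11% | 4.09% |
| 30% | 30 | 4.09% | 6.34% | 11.28% | 24.28% |
| 20% | 15 | 0.11% | 0.19% | 0.41% | 1.19% |
| 30% | 15 | 1.19% | 1.71% | 2.83% | 5.82% |

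With 30 patients the increase is at most 0.2 points from a 10% base, 0.2 to 3.9 points from 20%, and 2.2 to 20.2 points from 30%. These are upper figures, since they take every added event as procedure-related and as occurring in a patient with no other SAE.

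**What it would do to the DSMB meeting**

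The chance of at least one hospitalization-only patient is 1 − (1 − *h*)ⁿ. For *h* = 2%, 5% and 10% it is 18%, 40% and 65% with 10 patients, and 45%, 79% and 96% with 30. So such an event may well occur. Under a misreading it would wait for the next scheduled meeting. These fall every 4 patients, or 4/15 × 12 = 3.2 months apart at the expected maximum of 15 patients a year, and 4/7.5 × 12 = 6.4 months at half that pace.

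**What would not change**

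The combined AE/SAE rate through POD 90 is the same under either reading, because all AEs are recorded in that window. Section 2.1 sets the primary objective in the immediate post-operative period.

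**The case for a change.** The strongest opposing argument is that, if AE is merely the umbrella term, the sentence in 8.3 says nothing, since every grade is then an AE. It seems to gain content only if Grades I and II mean non-serious, in contrast to III to V. That is a fair reading of the pairing, and a coder working from the grade table alone could adopt it. But the sentence can do another job. Grade I takes in any departure from the expected course, even one needing no treatment, and 8.3 can be read as saying that these too count as AEs. And even on the contrasting reading, a general label in 8.3 would have to override an explicit outcome rule in the section that defines an SAE.

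What stands is that no sentence states how the two tests combine, and that the recording after POD 90 depends on the answer. Two things limit the risk. Infection within 90 days, pneumothorax and bronchopulmonary plug are named safety endpoints in the synopsis whatever their SAE status. After POD 90, each scheduled visit, and any unscheduled one, includes a complications review, and section 8.9 has subjects asked about care sought between visits. Those steps would bring a late hospitalization to light, though they do not by themselves put it into the adverse event record. It is also true that meetings tied to enrollment end when enrollment does; after that only the general commitment to meet regularly remains.

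**Conclusion.** The concern does not call for a change. The passages do not contradict each other: followed as written, 8.4 already makes a Grade I or II event with a listed outcome an SAE. The missing statement of how the outcome list and the grades combine is a detail that study staff can fill sensibly from 8.4 itself. A cross-reference in 8.3 would do no harm, but nothing in the analysis depends on it.

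If the grades were nevertheless misread as decisive, the primary rate through POD 90 would be unaffected and DSMB review would be delayed rather than lost. The halting probability would move by less than 4 percentage points at base SAE rates up to 20%. It would move materially only from a base of about 30% or more with close to 30 patients counted. The conclusion rests on reading AE as the umbrella term, which 8.2 and the recording plan support, and on assumed event rates, since the documents give none.
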